7.3 Study participants

7.3.1 Subject Distribution

Count the number of subjects who signed informed consent. Count the number of screen failures and randomized subjects.

Among all randomized subjects, calculate the number and percentage who completed the study and who withdrew early, along with reasons for early withdrawal.

Provide summaries by study site and list of subject distribution.

7.3.2 Protocol Deviations

For all enrolled subjects, calculate the number and percentage of subjects with major protocol deviations during the study.

Provide summaries by study site and a list of all protocol deviations or violations.

7.3.3 Analysis data set

For all enrolled subjects, calculate the number and percentage included in: Full Analysis Set (FAS), Per Protocol Set (PPS), and Safety Set (SS). Summarize reasons for exclusion from each analysis set.

Provide summaries by study site and a list of subjects included in each analysis set.

7.3.4 Demographics and Baseline Characteristics

Analysis will be based on the Full Analysis Set (FAS).

Demographics: For continuous variables (e.g., age): report number of subjects, mean, standard deviation, median, Q1, Q3, minimum, and maximum.

For categorical variables (e.g., sex, ethnicity): report frequency and percentage for each category.

Provide summaries by study site and a list of demographic data.

Diabetes Diagnosis History: Count and report the number and percentage of newly diagnosed type 2 diabetes patients and those who used antidiabetic drugs in the past 3 months. Provide descriptive summary of diabetes duration.

List of newly diagnosed type 2 diabetes patients.

Hypoglycemia History:

Count and report the number and percentage of subjects with hypoglycemia episodes within 1 year prior to screening.

List of subjects with hypoglycemia history.

Medical History: Count and report the number and percentage of subjects with relevant medical history.

Use MedDRA/C [v27.0] coding, summarized by SOC/PT. Present SOC and PT in descending order of total percentage.

List of subjects with medical history.

7.3.5 Concomitant Medications:

Analysis will be based on the Full Analysis Set (FAS).

Concomitant medications will be coded using WHODrug GLOBAL (B3) C [V2024MAR].

Medications will be summarized by ATC classification.

A list of subjects and their concomitant medication usage will be provided.

7.3.6 Treatment Compliance

Analysis will be based on the Full Analysis Set (FAS).

For medication adherence during each follow-up visit, the following four aspects are summarized:

1. Calculate the number of cases and percentage of each category of timely medication adherence for antidiabetic drugs since the last visit (never missed, rarely missed (no more than 3 times per week), frequently missed (3 or more times per week), almost never taken, and overdose).
2. Calculate the percentage of adherence and perform descriptive statistics on participants' adherence. Summarize the number of cases and percentages for each adherence category (<80%, 80%-120%, >120%).
3. Use the ATC4 classification according to the WHODrug GLOBAL (B3) C [V2024MAR] coding system to calculate the number of cases and percentages of antidiabetic drugs used at each visit, and provide a summary by center.
4. Using the ATC4 classification of WHODrug GLOBAL (B3) C [V2024MAR], calculate the number and percentage of cases for each category of polypharmacy (monotherapy, dual therapy, triple therapy) for antidiabetic drugs at each visit, and provide a summary by center. If the ATC4 classification is an oral combination antidiabetic drug, it should be counted as dual therapy.

List the medication usage list for diabetes treatment and the diabetes treatment regimen list.

7.4 Efficacy Analysis

7.4.1 Primary Endpoint Analysis

Analysis will be conducted using both the Full Analysis Set (FAS) and Per Protocol Set (PPS).

Calculate the number of participants, percentage, and 95% CI of participants with HbA1c < 7% at visit 5 (baseline 84 ± 3 days) in the intervention group and control group, respectively. Calculate the 95% CI of the difference in proportions between the two groups (intervention group - control group). Use the chi-square test or Fisher's exact probability test to compare the proportions of participants with HbA1c < 7% between groups. The 95% CI was calculated using the Wald method.

Sensitivity analysis of primary efficacy endpoints: Using the CMH method that accounts for center effects, compare the proportion of subjects with HbA1c < 7% between groups.

List the subjects with HbA1c < 7% at Visit 5.

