3.1 Study Population, Inclusion Criteria, Exclusion Criteria, and Withdrawal Criteria

3.1.1 Study Population:

A total of 200 newly diagnosed type 2 diabetes patients will be enrolled based on the 1999 WHO diagnostic criteria.

3.1.2 Inclusion Criteria:

- 3.1.2.1 Patients voluntarily signed informed consent forms;
- 3.1.2.2 Age between 20 and 70 years;
- 3.1.2.3 Newly diagnosed type 2 diabetes patients with a disease duration of less than 1 year and no use of antidiabetic medications in the past 3 months; HbA1c ≥7.5% and <10.5%;

3.1.3 Exclusion criteria:

- 3.1.3.1 Presence of proliferative retinopathy or macular degeneration requiring treatment, painful diabetic neuropathy, diabetic foot, diabetic ketoacidosis, or hyperglycemic hyperosmolar state within the past 3 months;
- 3.1.3.2 History or presence of the following conditions within the past 6 months:
 - 1) Decompensated heart failure (NYHA class III or IV);
 - 2) Myocardial infarction, coronary artery bypass grafting, or coronary artery stent implantation; 3) Uncontrolled severe arrhythmia, and deemed unsuitable for participation in this clinical trial by the investigator;
 - 4) Hemorrhagic stroke or ischemic stroke, and deemed unsuitable for participation in this clinical trial by the investigator;
- 3.1.3.3 Laboratory test results meet any of the following criteria:
 - 1) Alanine transaminase (ALT) or aspartate transaminase (AST) > 3 times the upper limit of normal;

- 2) Total bilirubin > 2 times the upper limit of normal;
- 3) Hemoglobin < 100 g/L;
- 4) Total protein < 60 g/L;
- 5) Albumin < 30 g/L;
- 6) Estimated glomerular filtration rate (eGFR) <60 mL/min/1.73 m²;
- 3.1.3.4 Any condition that may cause red blood cell instability and affect HbA1c testing, such as thalassemia or hemolytic anemia;
- 3.1.3.5 Currently has uncontrolled thyroid dysfunction;
- 3.1.3.6 Has received systemic steroid therapy within the past month (excluding inhaled or topical use);
- 3.1.3.7 Pregnant or lactating women;
- 3.1.3.8 Two or more episodes of severe hypoglycemia within the past year prior to screening;
- 3.1.3.9 Patients whom the investigator deems require initiation of sulfonylurea, glinide, insulin, or insulin analog therapy;
- 3.3.3.10 Patients currently receiving calcium hydroxybutyrate treatment or with a condition requiring calcium hydroxybutyrate treatment, and who the investigator believes may require additional calcium hydroxybutyrate treatment in the near future.

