5.7 Safety analysis

Safety analysis was conducted using the safety analysis set (SS) as the primary analysis set. Adverse events (AEs) and serious adverse events (SAEs) occurring during treatment were summarized and analyzed by treatment group based on

their incidence rates and severity, and classified according to major system organs and medical terminology. Other safety data, including laboratory test results, were analyzed and compared with the screening period using descriptive methods.

6. Case allocation among study centers

This trial uses a competitive enrollment method, and the case allocation plan for each study center is each center will recruit 10 subjects in the control group and 10 subjects in the intervention group, for a total of 100 subjects in the control group and 100 subjects in the intervention group.

7. Subject Protection (if applicable)

This clinical trial will be conducted in accordance with the Declaration of Helsinki (2008 revised edition) and relevant Chinese laws and regulations governing clinical trials. Prior to the commencement of the trial, approval must be obtained from the Ethics Committee, and the trial may only be conducted after such approval has been granted. Any modifications to the trial protocol must be approved by the Ethics Committee prior to implementation.

Prior to the start of the trial, an informed consent form must be provided to each participant, and they must be instructed to read it carefully. The study physician is responsible for explaining the contents of the informed consent form in detail and addressing any questions the participant may have. The participant must be fully informed about the purpose of the trial, the treatment regimen, laboratory tests, potential risks, and their rights and benefits. Participants must also be informed that they may choose alternative treatment options and withdraw from the trial at any time without facing any adverse consequences. Each patient must voluntarily sign the informed consent form before entering the trial. The study physician must ensure that all informed consent forms are properly stored in the study records. The privacy of participants must be protected, and information related to their participation in the trial must not be disclosed without authorization. If necessary, the drug regulatory authorities, ethics committee, or sponsor may review the records of participants in the trial in accordance with applicable regulations.

8. Research Management

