8.3 Specimen Collection, Storage Facilities, and Laboratory Premises

The specimen collection, storage facilities, and laboratory premises for this trial are located at each center.

9 Requirements for Reporting Adverse Events

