3.3. Sample size

Each group (Intervention and Control) will include 100 subjects.

The sample size was determined based on a preliminary single-center pilot study (n=40), which showed that the proportion of subjects achieving HbA1c < 7% after 3 months was 76.9% in the intervention group and 46.2% in the control group (p = 0.226).

Assuming:

- $\alpha = 0.05$ (two-sided significance level)
- Power = 0.8
- Effect size = 30% difference between groups

Considering factors such as:

- Follow-up completion rate in the pilot study (72.5%)
- Multicenter design

The target sample size was calculated to be 100 subjects per group.

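### The primary HbA1c <7% comparison leaves out screening HbA1c: the test is valid, but adjustment would add precision at no data cost, by an amount the documents do not fix

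*SAP*

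**What the plan says.** **Primary test.** SAP 7.4.1 instructs: "Use the chi-square test or Fisher's exact probability test to compare the proportions of participants with HbA1c < 7% between groups". Its 95% CIs use the Wald method. Protocol 5.5 names the same tests.

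**Centre.** Both documents keep centre for a sensitivity analysis. The SAP wording is "Using the CMH method that accounts for center effects, compare the proportion of subjects with HbA1c < 7% between groups". Neither section states an adjusted effect estimate to go with it.

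**Screening HbA1c.** Eligibility requires "HbA1c ≥7.5% and <10.5" per cent (Protocol 3.1.2.3). The value is obtained at Visit 1 (Protocol 3.3.1.5), and SAP section 6 admits to the FAS only participants with a baseline measurement of the primary outcome. It is used for the change-in-HbA1c secondary endpoint, but in no analysis of the primary endpoint in the available text.

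**Allocation.** Protocol 3.2 and SAP 3.1 describe block randomisation at 1:1 and name no stratification factor. Protocol section 6 says enrolment is competitive and also that "each center will recruit 10 subjects in the control group and 10 subjects in the intervention group". Laboratories are local: "The specimen collection, storage facilities, and laboratory premises for this trial are located at each center" (Protocol 8.3).

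**The concern.** Success is HbA1c below 7% at week 12. A participant entering at 7.5% needs a fall of just over 0.5 points; one entering near 10.5% needs about 3.5. Starting value should therefore say a good deal about who succeeds. Leaving a prognostic covariate out of the analysis of a binary outcome leaves its variation in the standard error of the risk difference.

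Two things are at stake. One is precision, which matters if the true effect is smaller than planned. The other is credibility: with 200 participants and no stated stratification on HbA1c, the arms may differ by chance at screening. If adjustment is chosen only after that is seen, the choice is open to challenge.

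**Working it through.** **1. The plan's own sample size.** Inputs from SAP 3.3: alpha 0.05 ("two-sided significance level"), power 0.80, "Effect size = 30% difference between groups", pilot rates 76.9% and 46.2%, completion 72.5%, 100 per group.

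n = [1.960·√(2p̄(1−p̄)) + 0.842·√(p₁(1−p₁) + p₀(1−p₀))]² / (p₁−p₀)²

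With p₁ = 0.762, p₀ = 0.462 and p̄ = 0.612, n = (1.960 × 0.689 + 0.842 × 0.656)² / 0.09 = 40.2, so 41 per group; 41/0.725 gives 57. Pilot rates give 39 and 54; 65% v 35% gives 43 and 60. Continuity correction raises the inflated figures to 63-68. The stated 100 is not reproduced; SAP 3.3 also cites the multicentre design, without a figure. So there is slack at 30 points.

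**2. Unadjusted power (same normal approximation).** 72 per group is about 72.5% of 100.

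| True difference | 100 per group | 72 per group |
|---|---|---|
| 30 points | 0.992-0.996 | 0.957-0.973 |
| 20 points (66.2% v 46.2%) | 0.82 | 0.68 |
| 15 points (61.2% v 46.2%) | 0.57 | 0.44 |

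The 30-point row covers 65% v 35% up to the pilot rates.

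**3. How firm is 30 points?** The pilot p = 0.226 reproduces as Fisher's test on 10/13 v 6/13. The Wald 95% CI is 0.308 ± 1.96 × √(0.769 × 0.231/13 + 0.462 × 0.538/13) = 0.308 ± 0.355, about −5 to +66 points. An effect of 15-20 points is compatible with it.

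**4. Dropouts.** SAP 4.1.1 divides by the whole analysis set and SAP 7.2.1 imputes nothing. Read literally, a missing Visit 5 value counts as a non-success. Pilot rates then become 0.769 × 0.725 = 55.8% and 0.462 × 0.725 = 33.5%, a 22.3-point difference with power about 0.89 at 100 per group. The other reading is completers only, about 72 per group. Both are carried forward.

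**5. Assumptions not in the documents.** Ten centres (100/10), arms balanced within centre, screening HbA1c uniform on 7.5-10.5. Log-odds slope 0.5 to 1.5 per HbA1c point: across the 3-point range that is an odds ratio of e^1.5 ≈ 4.5 to e^4.5 ≈ 90. Centre SD 0 to 1.0 on the logit scale.

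**6. Simulated gain from adjusting for HbA1c and centre.**

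- Dropouts as failures, independent of HbA1c, pilot rates: variance cut roughly 2-10%; power about 0.90 becomes 0.90-0.93. For a 15-point effect, power rises 1-6 points (58% to 61% in the middle case).
- Completers only: variance cut roughly 1-25%. For a 20-point effect, power of about 0.67-0.69 becomes 0.71-0.84.

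A variance cut of v is worth 1/(1−v) − 1 more participants: about 2-11% on the first reading and 1-33% on the second.

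**7. HbA1c adjustment against CMH by centre (completers, 72 per group).** Adjustment here is for HbA1c alone. The slope is per SD of HbA1c; one SD of the assumed distribution is 3/√12 = 0.87 points, so 1.5 per SD is 1.73 per point, beyond the range in step 5.

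| Effect | Slope per SD | Centre SD | Chi-square | CMH | HbA1c-adjusted | Variance cut |
|---|---|---|---|---|---|---|
| 20 | 0 | 1.0 | 0.701 | 0.748 | 0.697 | −1.4% |
| 20 | 1.0 | 0 | 0.697 | 0.687 | 0.775 | 18.7% |
| 20 | 1.0 | 1.0 | 0.697 | 0.729 | 0.752 | 13.0% |
| 20 | 1.5 | 0.5 | 0.692 | 0.685 | 0.836 | 31.2% |
| 30 | 1.0 | 0 | 0.966 | 0.964 | 0.985 | 16.7% |
| 30 | 1.5 | 0.5 | 0.965 | 0.965 | 0.994 | 28.2% |

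At 30 points the gain is at most about 3 points. Monte Carlo error on power is about 1 point.

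**8. Validity.** Simulated type I error of the chi-square was mostly 4-6%.

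**The case against.** The strongest reply is that nothing is broken. Randomisation makes the unadjusted comparison valid, and its interval already allows for chance imbalance. At the planned effect, power is 96% or more on completers and over 99% with all 100 per group. Every figure for the gain rests on assumed slopes and centre spreads, and with no prognostic value there is no gain. Counting dropouts as failures dilutes the covariate, and most of the gain disappears. Centre is already covered by a pre-specified CMH test. All of this stands, and it is why this is an efficiency point.

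It does not remove the case for adjustment. The 30-point effect rests on 26 analysed pilot participants, an effect of 15-20 points is compatible with them, and there precision counts.

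A reader might go further in three ways that the documents do not support:

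- *The chi-square is conservative because arms are balanced 10 to 10 within centre.* In some runs with centre SD 1.0 and exact balance, its type I error was 3.3-4.0%. But no stratification by centre is stated, and enrolment is competitive. A centre SD of 1.0 would put centres one SD either side of 50% at about 27% and 73%; nothing supports that spread.
- *Making the centre-stratified CMH test primary is enough.* Step 7 shows it within about a point of the chi-square at centre SD 0 to 0.5, and sometimes below it.
- *The loss is a firm figure, such as a 16% variance cut and power of 59% instead of 64%.* That needs a 15-point effect, half the planning value, and a slope acting on the composite of dropout and control.

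**Conclusion.** The point holds as a missed improvement. The primary analysis omits a covariate that is complete in the FAS and plausibly strong, and the plan has no pre-specified adjusted estimate to turn to if the arms differ at screening. The test is not invalid, and a 30-point effect would be detected either way.

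The variance cut is roughly 2-10% or 1-25%, depending on how missing Visit 5 values enter. Power for a true effect near 15-20 points rises by between almost nothing and about 15 points. These ranges rest on the slope and centre-spread assumptions in step 5. Confidence is high on what the plan says and low on the exact gain.

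Two limits apply. The SAP is based on Protocol Version 3.0, while the protocol available is Version 2.0. The part of the SAP between 7.2.2 and 7.3 and the separate table shells were also not available.

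**What to change.** In SAP 7.4.1, before outcomes by arm are examined, pre-specify as primary a logistic model with arm, continuous screening HbA1c and centre. Standardise it to a risk difference (intervention minus control) with a robust-variance 95% CI. The variance method should be named, because a model-based version ran slightly high in simulation (type I error 6.2-7.3%). State a pooling rule for small centres, and say whether a missing Visit 5 value counts as a non-success, since the gain depends on it.

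Keep the unadjusted chi-square and the CMH test as sensitivity analyses. List the change in SAP 7.7 and align Protocol 5.5; otherwise the two documents would disagree on the primary test.

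The cost is a few lines of text, standard SAS code and ethics approval of the protocol amendment (Protocol section 7). No new data are needed.

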7.4.2 Secondary Endpoint Analysis

Analysis will be conducted using both FAS and PPS.

*** Proportion of participants with HbA1c < 6.5% at Visit 5 (baseline 84 ± 3 days)**

Calculate the number of participants, percentage, and 95% CI of participants with HbA1c < 6.5% at Visit 5 (baseline 84 ± 3 days) in both the intervention group and the control group. Calculate the 95% CI of the difference in proportions between the two groups (intervention group – control group). Use the chi-square test or Fisher's exact probability test to compare the proportions of participants with HbA1c < 6.5% between groups.

List the participants with HbA1c < 6.5% at Visit 5.

*** Proportion of participants with HbA1c < 6% at Visit 5 (baseline 84 ± 3 days)**

Calculate the number of participants, percentage, and 95% CI of participants with HbA1c < 6% at Visit 5 (baseline 84 ± 3 days) in the intervention group and control group, respectively. Calculate the 95% CI for the difference in proportions between the two groups (intervention group - control group) and use the chi-square test or Fisher's exact probability test to compare the proportions of participants with HbA1c < 6% between the two groups.

List the participants with HbA1c < 6% at visit 5.

*** Decrease in HbA1c at Visit 5 (baseline 84 ± 3 days).** Calculate the decrease in HbA1c for the intervention group and control group at visit 5 compared to the screening period, as well as the percentage change. Use t-tests or Wilcoxon rank-sum tests for intergroup comparisons. Among them, the percentage change in HbA1c at Visit 5 compared to the screening period = $(\text{HbA1c at Visit 5} - \text{HbA1c at the screening period}) / \text{HbA1c at the screening period} \times 100\%$.

*** Hypoglycemia Incidence and Frequency:**

Calculate the number of episodes, total number of episodes, and percentage of participants in the intervention group and control group who experienced hypoglycemia during each visit (V3A—control group visit/V3B—intervention group visit, V4). For hypoglycemia incidence rates, use chi-square tests or Fisher's exact probability test for between-group comparisons.

List the hypoglycemia episodes experienced by participants at each visit.

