3.3.5 Visit 4 – Follow-up period (baseline ± 3 days)

- 3.3.5.1 Physical examination (measurements: weight, waist circumference, blood pressure, pulse rate);
- 3.3.5.2 Blood samples collected and frozen for storage in both Group A and Group B (to be measured for GA at the end of the study);
- 3.3.5.3 Record all data (medication changes, occurrence of hypoglycemia, other safety events).
- 3.3.5.4 The study physician conducting this visit should generally not adjust medications. However, adjustments may be made if the patient reports adverse events related to medication. Since this study excludes sulfonylureas, glinides, insulin, and insulin analogues, the theoretical risk of hypoglycemia is extremely low. If the patient reports hypoglycemia within the past month, the cause must first be identified and appropriate management provided. If unexplained hypoglycemia occurs, the investigator may consider reducing the dose of oral hypoglycemic agents as appropriate.

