3.3.6 Visit 5 - Follow-up period (baseline: 84 ± 3 days)

- 3.3.6.1 Physical examination (measurements: weight, waist circumference, blood pressure, pulse rate);
- 3.3.6.2 Collect samples and perform relevant tests: fasting blood glucose, HbA1c, fasting C-peptide, fasting insulin, glycated albumin (GA); Complete blood count: red blood cells (RBC), white blood cells (WBC), platelets (PLT), hemoglobin (HGB);Liver and kidney function: total bilirubin (Tbil), alanine transaminase (ALT), aspartate transaminase (AST), total protein (TP), albumin, blood urea nitrogen (BUN) or urea (Urea), serum creatinine (Cr), uric acid (UA);Lipid profile: Total cholesterol (TC), triglycerides (TG), low-density lipoprotein (LDL-C), high-density lipoprotein (HDL-C);
- 3.3.6.3 Determine that the subject has completed the entire trial.
- 3.3.7 Each center measures GA frozen samples.

3.4 outcome measures

3.4.1 Primary endpoint:

Proportion of participants achieving HbA1c < 7% at Visit 5 (Week 12 \pm 3 days from baseline).

3.4.2 Secondary endpoints:

- 3.4.2.1 Proportion of participants achieving HbA1c < 6.5% at Visit 5.
- 3.4.2.2 Change in HbA1c levels from baseline to Visit 5.
- 3.4.2.3 Incidence and frequency of hypoglycemia
- 3.4.2.4 Changes in pancreatic β -cell function (HOMA- β = 20 × FINS / (FPG 3.5));
- 3.4.2.5 Changes in insulin resistance levels (HOMA-IR = FINS \times FPG/22.5);
- 3.4.2.6 Changes in body weight, waist circumference, and BMI;

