3.2 Study Procedures and Follow-up Schedule

The research steps and follow-up plan are shown in Figure 1 and Table 1.

[figure not shown]

Figure 1. Research process diagram

Table 1 Research flowchart

	Screening visits	Baseline [#]	Follow-up				Measurement of GA Frozen sample
Visit number	1	2	3A	3B	4	5	
visit time	Days -7 to 0	Day 0	4 weeks (baseline: 28 ± 3 days)	4 weeks (follow-up visit 3A + 5 days) [*]	8 weeks (baseline 56 \pm 3 days)	12 weeks (baseline 84 \pm 3 days)	Follow-up visit completed
informed consent	X						
Demographic information (name,	X						

gender, ethnicity, date of birth)							
Medical history ^a	X						
Physical examination ^b	X		X ^h	X ^g	X	X	
Collect samples and perform the following laboratory tests:							
Blood glucose-related tests ^c	X ⁱ					X	
Complete blood count ^d	X ⁱ					X	
Liver and kidney function ^e	X ⁱ					X	
lipids ^f	X ⁱ					X	
Blood or urine pregnancy test	X ⁱ						
Blood sample collection (for GA measurement)	X		X ^h		X		
Inclusion/exclusion criteria	X	X					
Confirm eligibility for enrollment		X					
Randomization		X					
Treatment plan		X					
Distribution of subject diaries		X	X ^h	X ^g	X		
Check and collect participants' report			X ^h	X ^g	X	X	
GA measurement			X ^g			X	
Adjust treatment plan			X ^h	X ^g	X		
Recording medication treatment	X	X	X ^h	X ^g	X	X	
Record and review		X	X ^h	X ^g	X	X	

(since the previous visit)						
(S) AE						
study termination					X	
Determination of GA in frozen samples						X

Notes:

- #If screening and baseline are conducted on the same day, all duplicate steps need only be performed once
- *It is best to conduct the visit within 3 days after the 3A visit, with a maximum of 5 days
- a. Medical history includes information such as disease course and treatment methods
- b. Physical examination includes: height, weight, waist circumference, blood pressure, pulse (screening period); weight, waist circumference, blood pressure, pulse (follow-up period)
- c. Blood glucose-related tests include: fasting blood glucose, HbA1c, fasting C-peptide, fasting insulin
- d. Complete blood count: red blood cells (RBC), white blood cells (WBC), platelets (PLT), hemoglobin (HGB)
- e. Liver and kidney function: total bilirubin (Tbil), alanine transaminase (ALT), aspartate transaminase (AST), total protein (TP), albumin, blood urea nitrogen (BUN) or urea (Urea), serum creatinine (Cr), uric acid (UA)

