7.5.2 Adverse Events (AEs)

Coding: All AEs will be coded using MedDRA/C [v27.0].

Summarize the number of cases, incidence rates, and frequency of adverse events, serious adverse events, adverse events related to drug therapy, serious adverse events related to drug therapy, and adverse events leading to withdrawal from the study that occurred during the research process.

Summarize adverse events, serious adverse events, adverse events related to drug therapy, serious adverse events related to drug therapy, and adverse events leading to withdrawal from the study according to SOC/PT and describe them in groups. If the same patient experiences multiple adverse events, count it as one case when calculating the incidence rate; if a patient experiences the same AE multiple times, count it as one case in the AE incidence rate calculation.

Severity of adverse events: Assess the severity of AEs as mild, moderate, or severe, and summarize the number of cases, incidence rate, and severity of adverse events for each severity level. If a subject experiences multiple AEs, the most severe AE is included in the analysis of the number of adverse events; if a subject experiences the same AE multiple times, the most severe occurrence is included in the analysis of the incidence rate for that severity level.

Adverse events related to drug therapy: Adverse events classified as “definitely related,” “likely related,” or “possibly related” to drug therapy.

Provide a summary table of adverse events by subcenter.

Provide a list of all types of adverse events.

7.5.3 Device Defects: Not applicable.

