7.7 Changes to the Planned Analyses

1. Changes in pancreatic β -cell function, insulin resistance levels, body weight, waist circumference, and BMI: Calculate the change in values at the end of treatment (V5) relative to the screening period. This has been changed to calculating both the change in values and the percentage change at the end of treatment (V5) relative to the screening period.
2. Add the statistical analysis of the proportion of patients with $\text{HbA1c} < 6\%$ at Visit 5 (baseline 84 ± 3 days) to the secondary endpoint measures.

8. References

- [a] National Medical Products Administration (NMPA). Good Clinical Practice for Medical Device Clinical Trials. May 2022.
- [b] Guidelines for Biostatistics in Drug Clinical Trials. June 2016.

[c] Guidelines for Data Management and Statistical Analysis Plans in Drug Clinical Trials. Announcement No. 63, 2021.

9. Statistical Chart Templates

Refer to the attached file “Asahi Kasei_GA_TFL_Mock shell_V1.0-20241009” and generate an independent file.

10. Data Set Programming INSTRUCTIONS

Refer to the attached file “Asahi Kasei_GA Project ADS Programming Specifications” and generate an independent file.

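### SAP 7.4.2 stops counting and comparing hypoglycemia at Visit 4, so the last four of twelve weeks are missing from a named secondary endpoint

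*SAP*

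**What the plan says.** - **SAP 7.4.2, hypoglycemia paragraph.** Episodes and percentages are to be calculated by group for participants "who experienced hypoglycemia during each visit (V3A—control group visit/V3B—intervention group visit, V4". Incidence is then compared between groups by chi-square or Fisher's exact test. The sentence on the test gives no window of its own. A by-visit listing is also requested, with no stated last visit.
- **Protocol 3.4.2.** The endpoint is "Incidence and frequency of hypoglycemia", with no time limit. SAP 4.1.2 repeats it and says of the secondary endpoints generally that they run from screening to Visit 5.
- **Table 1 (Protocol 3.3, SAP 3.2).** The row "Check and collect participants' report" is marked at Visits 3A (Group B), 3B (Group A), 4 and 5. Diaries are handed out at Visit 4, and (S)AEs since the previous visit are reviewed at Visit 5.
- **Protocol visit text.** At Visit 4 (3.3.5.3) the instruction is "Record all data (medication changes, occurrence of hypoglycemia, other safety events". Visits 3A and 3B have a similar line. Visit 5 (3.3.6) lists an examination, laboratory tests and the step "Determine that the subject has completed the entire trial", but no line on hypoglycemia.
- **Protocol 3.3.5.4, on Visit 4.** "The study physician conducting this visit should generally not adjust medications".
- **SAP 7.7.** Two changes are declared. One adds percentage changes for several continuous endpoints. The other begins "Add the statistical analysis of the proportion of patients with" and concerns HbA1c below 6%. Neither concerns hypoglycemia.

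**The concern.** Visit records look back: Table 1 reviews events since the previous visit, and Protocol 3.3.5.4 speaks of hypoglycemia over the preceding month. A list that ends at V4 therefore ends at about day 56, and episodes from then to day 84 enter neither the counts nor the test.

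Those four weeks matter for this design. Group A's treatment is adjusted from the GA result at Visit 3B, and further changes at Visit 4 are discouraged, so much of the exposure to the adjusted regimens falls after Visit 4. The HbA1c benefit would be measured at week 12, while hypoglycemia would be compared only to week 8. A reader who knows the protocol endpoint would reasonably take the reported figure as a 12-week result.

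A second ambiguity is that the SAP does not say whether the test is run per visit or cumulatively. If it is per visit, the first interval can end up to 5 days later in Group A (Visit 3B) than in Group B (Visit 3A). Cumulatively to V4, the nominal windows are equal.

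**Working it through.** The plan states no figure for this endpoint, so there is none to reproduce. The check compares the counted window with the follow-up window.

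**Inputs.** From Table 1: Visit 3A on day 28 ± 3, Visit 3B up to 5 days after 3A, Visit 4 on day 56 ± 3, Visit 5 on day 84 ± 3. The possible days are therefore:
- V3B: 25 to 36
- V4: 53 to 59
- V5: 81 to 87

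**Share of follow-up omitted** = (V5 − V4) / V5
- Nominal: (84 − 56)/84 = 28/84 = 33.3%
- Smallest: (81 − 59)/81 = 22/81 = 27.2%
- Largest: (87 − 53)/87 = 34/87 = 39.1%

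**Share of Group A's time after Visit 3B omitted** = (V5 − V4) / (V5 − V3B)
- Nominal, V3B on day 28: 28/(84 − 28) = 28/56 = 50.0%
- Nominal, V3B on day 33: 28/(84 − 33) = 28/51 = 54.9%
- Smallest: 22/(81 − 25) = 22/56 = 39.3%
- Largest: 34/(87 − 36) = 34/51 = 66.7%

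**Subjects not counted (illustration).** The documents give no hypoglycemia rate. Assume a constant 4-week risk q and complete follow-up. Incidence to week 8 is 1 − (1 − q)², and to week 12 it is 1 − (1 − q)³.

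| Assumed q | To week 8 | To week 12 | Not counted, per 100 |
|---|---|---|---|
| 0.5% | 1.00% | 1.49% | 0.50 |
| 1% | 1.99% | 2.97% | 0.98 |
| 2% | 3.96% | 5.88% | 1.92 |
| 5% | 9.75% | 14.26% | 4.51 |

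**Effect on the comparison (illustration).** Assume an 84-day control incidence of 5% with constant hazard h = −ln(0.95)/84, and a hazard in Group A that doubles after day 28. Incidence by day d is 1 − exp(−h·d) in Group B and 1 − exp(−h·[28 + 2(d − 28)]) in Group A.
- To day 84: 8.19% against 5.00%, a difference of 3.2 points. Power with 100 per arm is about 15%.
- To day 56: 5.00% against 3.36%, a difference of 1.6 points. Power is about 8%.

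The test is weak either way, but the shorter window halves the difference available to be seen.

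**Could the labels mean something else?** If V3A/V3B and V4 meant the interval starting at each visit, days 28 to 84 would be covered and days 0 to 28 lost. The look-back wording argues against this, and a third of follow-up would still be missing. For comparison, the adherence formulas in SAP 7.2.2 run over visits 3A/3B, 4 and 5.

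**The case against.** The strongest reply is that the SAP follows the protocol's own visit text: hypoglycemia is recorded at 3A, 3B and 4, Protocol 3.3.6 has no such line for Visit 5, and SAP 7.4.2 lists exactly those visits. On that view the root is a protocol inconsistency. This probably explains the gap. It does not justify it, because Table 1 in both documents collects reports and reviews events at Visit 5.

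Other points, and what stands of each:
- **Unseen documents.** The SAP rests on Protocol v3.0 and CRF v3.0, and only Protocol v2.0 could be read. SAP 7.2.3 was also not available for this check. This limits what can be said about the cause, and about whether SAP 7.7 should have declared a change. It does not alter the visit list in SAP 7.4.2.
- **Events may surface elsewhere.** Protocol 3.3.2.5 has investigators record suspected hypoglycemia in the CRF with dates and times, and SAP 7.5.2 summarises events over the whole study, down to "adverse events leading to withdrawal from the study that occurred during the research process". So the data are not necessarily lost. But those summaries are descriptive, and the SAP does not say how diary episodes map to adverse events.
- **Treatment after Visit 4.** Table 1 marks adjustment of the treatment plan at Visit 4, and Protocol 3.3.5.4 allows exceptions. In addition, some Group A participants have no change at Visit 3B. The omitted weeks are thus generally, not always, spent on the regimens in place after 3A/3B.
- **SAP 4.1.2.** Its sentence about changes from screening fits event counts poorly, so it is only supporting evidence.
- **Small consequence.** The endpoint is secondary, both arms are cut alike, and events are expected to be rare. All of that stands, and the 5% row in the table sits uneasily with the expected rarity.
- **Early withdrawal.** A window to Visit 5 needs a stated denominator, since SAP 7.2.1 imputes nothing. This is fair, although the same gap already exists at Visit 4.

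**Conclusion.** The concern holds. As written, SAP 7.4.2 gives an 8-week count and test for an endpoint that the protocol does not limit to 8 weeks. Nominally 28 of 84 days are left out (22 to 34 days across the allowed windows), including about half of Group A's time after Visit 3B. These shares follow from the visit schedule alone, on the reading that each visit's record covers the time since the previous one.

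The number of affected participants missed cannot be derived from the documents. The range of about 0.5 to 4.5 per 100 depends entirely on the assumed 4-week risks and on complete follow-up, and the true number may be small. The primary analysis is unaffected. This should be corrected before the analysis is run, because the omission is explicit, undeclared and easy to repair.

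**What to change.** 1. Add V5 to the visit list in SAP 7.4.2 and to the table shells.
2. Make the between-group comparison the proportion with at least one episode from randomisation to Visit 5, and report total episodes over the same period. State the denominator and how participants who leave before Visit 5 are handled.
3. Keep the by-visit table as description only, because the first interval can end up to 5 days later in Group A.
4. Reconcile Protocol 3.3.6 with Table 1 on recording hypoglycemia at Visit 5.
5. If the CRF has no Visit 5 hypoglycemia field, state in the SAP that these episodes are derived from the diary or adverse event records, and how.
6. If V5 was left out deliberately, declare that in SAP 7.7 with the reason, and label the result as covering the period to Visit 4.

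The cost is a short edit to the SAP and shells plus one protocol reconciliation. Deriving Visit 5 episodes from diaries or adverse event records would add some programming. No extra visit or test is needed.
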